6.4 Duration of Therapy

6.4.1 Criteria for the Discontinuation of Treatment (“Off Treatment”)

Patients may withdraw from treatment or the study overall at any time at their own request, or they may be withdrawn at the discretion of the Investigator for safety, behavioral reasons, or the inability of the patient to comply with the protocol-required schedule of study visits or procedures.

In addition to the drug-specific discontinuation criteria listed in Dose Modification Section, the following will result in treatment discontinuation:

- Adverse events or intercurrent illness that in the opinion of the investigator warrants the subject's withdrawal from study treatment

- The subject or legally authorized representative requests to discontinue the study treatment and/or study procedures
- Salvage treatment failure defined as radiographic progression per PCWG3 criteria OR RECIST 1.1. Patients taken off treatment for treatment failure will continue to be followed for toxicity assessments only every 6 months.
- Failure to initiate adjuvant radiotherapy within 4 months of completion of salvage therapy (oligometastasectomy and/or bone radiotherapy).
- Patient refused further treatment
- Significant noncompliance with the protocol schedule or treatment administration in the opinion of the investigator
- Clinical deterioration that, in the opinion of the investigator, increases the risk to the subject

Surgery may be aborted if unforeseen complications arise.

Radiation therapy courses may be shortened in case of RTOG Grade III-IV or persistent (≥ 2 weeks) Grade II toxicities. Continuation of treatment during Grade III toxicities may be allowed if the patient is benefiting as assessed by the treating investigator.

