10.3 Time to Recurrence

CT scans and optional bone scans will take place every 6 months for the first year after completion of per-protocol directed therapy then annually thereafter for a total of 3 years.

The disease-free survival is defined as the time elapsed between study enrollment and first occurrence of confirmed radiographic disease progression as assessed according to the PCWG3 criteria (soft tissue by CT or MRI scans according to RECIST v1.1, bone metastasis by bone scan according to the PCWG3 criteria).

Soft tissue recurrence is defined by RECIST 1.1 as a $\geq 20\%$ increase and absolute ≥ 5 mm increase in the sum of diameters of target lesions (at most 5 lesions and 2 lesions per organ) OR the appearance of one or more new unequivocal lesions OR the unequivocal progression of existing non-target lesions. Soft tissue progression does not require confirmatory scans.

Bone progression is defined PCWG3 criteria as the appearance at any restaging scan of ≥ 2 new lesions which persist or increase at the confirmatory scan (to be performed ≥ 6 weeks later) OR, if ≥ 2 new lesions are observed at the first restaging scan, the appearance of ≥ 2 additional new lesions at the confirmatory scan (to be performed ≥ 6 weeks later).

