Appendix F- Prostate Cancer Clinical Trials Working Group 3 (PCWG3)

The PCWG3 was created to more accurately assess bone lesions and to describe PSA based progression. PCWG3 rules were designed to be used in conjunction with radionuclide ($^{90}\text{m}\text{Tc}$) bone scintigraphy and therefore should be used for all bone response assessments. Only bone lesions seen on bone scans will be followed for assessment of response.

Bone Assessments

Baseline Assessment

All bone lesions may be recorded as non-target lesions only and the number of lesions should be noted.

Response Assessment

While on treatment, follow-up scans should be assessed for progressive disease (PD), progressive disease unconfirmed (P Du), no progressive disease (Non-PD), no evidence of disease (NED), or non-evaluable (NE).

Table 1: Bone response assessment categories

Bone Response	Definition
PD	2 new lesions, not flare, persistent
P Du	2 new lesions, but confirmation is required by the second scan. The temporary marker of PD should be updated to PD or non-PD upon subsequent scans. If P Du is determined on the last scan, sponsor should update to PD upon analysis.
Non-PD	At least 1 bone lesion present, but not enough to trigger PD.
NE	Status of bone lesions cannot be determined.
NED	No lesions are seen on bone scan (either none at baseline or all have resolved).

Rules of Progressive Disease

- 2+2 Rule: If 2 new lesions appear on the first scan after the initiation of treatment, the response is classified as P Du and another scan is performed ≥ 6 weeks.
 - If the next scans show at least 2 new bone lesions in addition to those seen in the prior scan, the prior scan is to be considered confirmed PD.
 - If the next scan does not show at least 2 additional new bone lesions the lesions seen on the prior scan are considered pre-existing lesions. The bone response on the prior scan is updated to non-PD and new lesions seen on the first scan are ignored.
- Once outside of the flare window (the first 12 weeks of treatment) the appearance of new lesions must be confirmed with a second scan ≥ 6 weeks after the first scan.
 - If ≥ 2 new lesions appear on a scan the scan will be classified as P Du until a second scan confirms lesion persistence.

- If lesions are persistent on the second scan, the prior response will be updated to PD.
- If the lesions disappeared on the second scan, the prior response is updated to non-PD.

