- If 1 new bone lesion is seen on one scan classifying the scan as non-PD, but the following scan shows an additional new lesion (2 new lesions total between subsequent scans) the second scan will be classified as PD.
- Diffuse skeletal tumor involvement may result in a superscan. In this case, distinguishing between individual new bone lesions may be impossible. If a superscan occurs after baseline, the response will be considered PD and no further confirmation scans are required.

PSA Progression

PSA should be monitored at the beginning of every cycle. Any rise in PSA during the first 12 weeks of treatment should be monitored but should not be deemed evidence of progression. Record the percent change from baseline at 12 weeks. After a decline from baseline: record time from start of therapy to first PSA increase that is $\geq 25\%$ and ≥ 2 ng/mL above the nadir, and which is confirmed by a second value ≥ 3 weeks later (i.e., a confirmed rising trend).

Nodal and Soft Tissue Progression

Nodal and soft tissue documentation, tracking, and determination of progression will follow RECIST 1.1.

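### Appendix F counts one new bone lesion plus one more on the next scan as progression without confirming the second, while Section 10.3 requires persistence, so time to recurrence has two unreconciled definitions

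*Combined protocol and SAP*

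**What the plan says.** Appendix F, under its rules of progressive disease, deals with a single new lesion followed by another on the next scan: "the following scan shows an additional new lesion (2 new lesions total between subsequent scans) the second scan will be classified as PD". The bullet goes straight to PD.

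Elsewhere Appendix F asks for persistence:
- Table 1 defines PD as "2 new lesions, not flare, persistent".
- Outside the 12-week flare window, "the appearance of new lesions must be confirmed with a second scan ≥ 6 weeks after the first scan".
- For lesions seen together, "If ≥ 2 new lesions appear on a scan the scan will be classified as P Du until a second scan confirms lesion persistence", and "If the lesions disappeared on the second scan, the prior response is updated to non-PD".
- Table 1 adds that a P Du on the final scan is turned into PD at analysis.

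Section 10.3 defines bone progression as two or more "new lesions which persist or increase at the confirmatory scan", that scan being at least 6 weeks later. Its only alternative is the 2+2 route from the first restaging scan. It does not describe a one-plus-one sequence.

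Sections 1.2.3, 10.3 and 11.3 (item 3) all call the endpoint confirmed radiographic progression. Item 3 plans Kaplan-Meier analysis for all evaluable patients and for each Arm. No section says whether 10.3 or Appendix F governs.

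**The concern.** Both texts define the event for the same Kaplan-Meier curves. An assessor working from Appendix F records an event at the second scan of a one-plus-one sequence. An assessor working from 10.3 either waits for a confirmatory scan or does not recognise the sequence at all. The same images can therefore give an event, a later decision or no event, depending on which page is open. The trial is meant to supply reference figures for this population (Section 2), so the event definition has to be reproducible.

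The choice can also affect what data exist afterwards. The footnotes to the Section 8 calendars recommend routine bone scans only for patients without evidence of progression. Recording PD at the second scan may thus remove a later scan that would have shown whether the second lesion persisted.

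**Working it through.** The plan gives no figure for bone progression. Its only design figure, the exact 95% interval of 12% to 54% for 6/20, concerns PSA response; it recomputes to 11.9% to 54.3% and plays no part here. The check is to apply each written rule to the same two lesions.

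Inputs: the Appendix F rules and Table 1; the two clauses of 10.3; the recommended bone scans at 6 and 12 months after all treatment and then yearly for two more years (Section 8 footnotes), that is, months 6, 12, 24 and 36. All four fall outside the 12-week flare window. For lesions seen together, the table takes a scan after the first restaging scan, so that the 2+2 rule does not interfere.

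| Lesions | What follows | Appendix F | Section 10.3 |
|---|---|---|---|
| Both on one scan | both persist | PD at that scan | event |
| Both on one scan | both resolve | non-PD | no event |
| Both on one scan | no further scan | P Du, made PD at analysis | unconfirmed |
| One, then one more | second does not persist | PD at second scan | no event |
| One, then one more | both persist | PD at second scan | event if *new* is cumulative; no event if counted per scan |
| One, then one more | no further scan | PD at second scan | unconfirmed at best |

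Row 4 is a direct contradiction: fewer than two new lesions persist, so 10.3 has no event, while Appendix F has already recorded one. Row 5 turns on an undefined term in 10.3. Row 6 differs as well, although the last-scan rule in Table 1 gives the same end result for lesions seen together (row 3).

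Example: one new lesion at month 6 and another at month 12. Appendix F records PD at month 12. Under 10.3 nothing is confirmed until a scan at least 6 weeks after that. If no dedicated confirmatory scan is done, the next recommended one is at month 24.

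Dating is also open. For lesions seen together, Appendix F updates the earlier scan to PD once they persist. Section 10.3 does not say whether the event takes the date of the scan showing the lesions or of the scan confirming them.

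Size: a Kaplan-Meier step is S(t−) × 1/(number at risk). With 20 at risk and no earlier event or censoring, this is 1 × 1/20 = 0.05, or 5 percentage points. In an Arm of n subjects it is 100/n points, which is larger because n is below 20 when subjects are spread over Arms. The plan sets no Arm sizes.

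**The case against.** The best defence is that confirmation is already implied. Table 1 says persistent, the post-flare rule says new lesions must be confirmed, and the endpoint is called confirmed. The one-plus-one bullet may be a sub-rule of the post-flare rule whose indentation was lost in the text available for review. The superscan bullet beside it waives further scans expressly, and the one-plus-one bullet does not. This shows that a waiver may not have been intended. It does not remove the conflict: the bullet assigns PD although P Du exists for exactly this situation.

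Second, recommended scans are 6 to 12 months apart, so a first lesion still visible at the second scan has been re-imaged well beyond 6 weeks. That stands. Only the second lesion is then unconfirmed.

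Third, 10.3 may intend a cumulative count, in which case two persisting lesions agree with Appendix F. That is possible, but 10.3 does not say so, and row 4 would remain.

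Fourth, the consequences are modest. Bone scans are recommended, optional or done if clinically indicated (Sections 8, 9.3 and 10.3), and Section 11.3 describes every analysis as descriptive and exploratory. That also stands, and it limits the weight of the point.

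**Conclusion.** The two endpoint definitions conflict and should be reconciled. A second lesion that does not persist is an event under the one-plus-one bullet and no event under 10.3. When both lesions persist, 10.3 leaves the call open. The effect is limited to time to recurrence, at 5 points per reclassified subject of 20 under the no-censoring assumption above. The primary PSA endpoint is unaffected.

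Three stronger readings are tempting, and the documents do not support them:
- A reader might infer that scan timing alone always decides the result. Within Appendix F it does not. If both lesions persist after the first restaging scan, or if P Du falls on the last scan, both routes end as PD. Two lesions together on the first restaging scan raise the 2+2 rule, which is a separate matter.
- A reader might try to estimate how many false events the bullet creates. If each of four scans independently shows one transient focus with an assumed probability q of 5%, 10% or 20%, the chance of two adjacent positive scans is 1 − [(1−q)^4 + 4q(1−q)^3 + 3q²(1−q)²] = 0.7%, 2.8% or 10.4%. The chance of at least one such subject in 20 is then 14%, 43% or 89%. But q has no source in the documents, all four optional scans must be done, and the first focus must have vanished yet still be counted. If it must still be visible, this model gives no events. The frequency cannot be estimated.
- A reader might infer loss of follow-up through Section 6.4.1, which has "Salvage treatment failure defined as radiographic progression per PCWG3 criteria OR RECIST 1.1" and then toxicity follow-up only. That text concerns patients taken off treatment. On the recommended schedule a one-plus-one call arises no earlier than month 12 after all treatment has ended, so the link is weak.

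**What to change.** For the endpoint analysis, make Appendix F and 10.3 give the same call and the same date:

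1. In Appendix F, classify the second scan of a one-plus-one sequence as P Du, becoming PD only if persistence is shown at least 6 weeks later. This matches the confirmed endpoint already stated.
2. Date a confirmed event to the scan on which the second lesion appeared.
3. In 10.3, state whether the count of two new lesions is cumulative from a reference scan, and name that scan.
4. State how this works with the Table 1 rule that P Du on the last scan becomes PD at analysis. Without this, an unconfirmed one-plus-one on the final scan would still be counted, and step 1 would change nothing for it.
5. Say which text governs if the two still differ.

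Section 6.4.1 refers to the same criteria, so it should be checked against the reconciled wording. No clinical rule is proposed here.

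The cost is a few sentences of protocol text. Some events will be assigned later, and an occasional subject will need a confirmatory scan that the general confirmation rule already expects.
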